11.3. PHARMACODYNAMICS

Not applicable.

11.4. PHARMACOKINETICS

Not applicable.

12. PRIOR AND CONCOMITANT TREATMENTS

At Visit 1 (Screening), all prior and concomitant medications, including antibiotics, and over-the-counter products used by an individual subject within 1 month prior to Screening Visit (Visit 1) will be documented in the eCRF.

During all subsequent clinical visits, the Investigator will document any changes in concomitant medications.

The following concomitant treatments are permitted from Visit 1 to Visit 4 (end of IMP treatment) or unscheduled Deterioration Visit:

- Appropriate treatment(s) for any respiratory tract disease, that in the investigator's opinion will not interfere with the measurements contributing to the efficacy outcomes, such as: corticosteroids (inhaled or systemic), bronchodilators, antibiotics (in case of co-administration, the i.v. antibiotic should be administered separately).
- Appropriate treatment(s) for any other underlying disease, that in the investigator's opinion will not interfere with the measurements contributing to the efficacy outcomes
- If co-treatment with parenteral nitroglycerin is needed the patients should be monitored for potential hypotension, which may be severe and may be indicated by the presence of headache
- If one or more treatments interfering with the measurements contributing to the primary efficacy outcomes are deemed necessary, the patient should not be randomized or should be discontinued from the study

The following concomitant treatments are not permitted from Visit 1 to Visit 4 (end of IMP treatment) or unscheduled Deterioration Visit:

- Expectorants
- Antitussive agents
- Sedatives
- Traditional Chinese Medicine (TCM) treatments.

All concomitant medications will be recorded and analysed as described in [Section 20.4.3.3](#).

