2. (For female patients) ongoing pregnancy or lactation, or childbearing potential but unwillingness to adopt abstinence or contraception measures during the study
3. Intake of an investigational drug within 1 month before the screening visit
4. Use of expectorants or drugs with expectorant effect within 2 days before randomization visit

5. Diagnosis of active tuberculosis, lung cancer, pulmonary fibrosis, acute pulmonary thromboembolism or any other respiratory condition that might, in the opinion of the investigator, compromise the safety of the patient or affect the interpretation of the results
6. Medical history of and/or illness (including laboratory abnormality) and/or treatment that in the investigator's opinion may interfere with the patient's safety, compliance, or study evaluations
7. Serum ALT and/or AST more than 3 times above the upper limit of normal at screening visit
8. Serum creatinine more than 3 times above the upper limit of normal at screening visit
9. Addiction to alcohol or drugs
10. Mental illness, or other reasons for non-cooperation in the investigator's opinion

Outcome measures:

Efficacy variables

- Sputum viscosity, expectoration difficulty, sputum color and cough are assessed by means of ordinal categorical 4-point scales with 0 = best and 3= worst.

For each patient the assessment is to be carried out by the blinded rater on treatment days 1 (baseline), 3 and 7 in the morning between 7 am and 9 am before administration of study drug. Should a patient discontinue prematurely from the trial (including discharge from the hospital before day 7) an assessment should be conducted on the day of discharge whenever possible.

Scoring criteria are as follows:

	0	1	2	3
Sputum viscosity	Liquid (normal viscosity)	Fluid (mildly increased viscosity)	Viscous (moderately increased viscosity)	Sticky (severely increased viscosity)
Expectoration difficulty	No difficulty	Mild difficulty	Moderate difficulty	Marked difficulty
Sputum Color	Mostly white	Mostly pale yellow	Mostly dark yellow	Very dark yellow /green
Cough	No cough	Sporadic and mild cough	Moderate cough	Severe Cough

Adapted from [12].

- Sputum volume: patients will collect 24-hour sputum (morning to same time of the following morning) in a

graduated cup on treatment days 1 (Baseline), 3 and 7.
Volume will be expressed as mL/24h.

Safety variables

- Adverse events assessed for severity and seriousness.

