- Appropriate treatment(s) for any respiratory tract disease, that in the investigator's opinion will not interfere with the measurements contributing to the efficacy outcomes, such as: corticosteroids (inhaled or systemic), bronchodilators, antibiotics (in case of co-administration, the i.v. antibiotic should be administered separately).
- Appropriate treatment(s) for any other underlying disease, that in the investigator's opinion will not interfere with the measurements contributing to the efficacy outcomes
- If co-treatment with parenteral nitroglycerin is needed the patients should be monitored for potential hypotension, which may be severe and may be indicated by the presence of headache
- If one or more treatments interfering with the measurements contributing to the primary efficacy outcomes are deemed necessary, the patient should not be randomized or should be discontinued from the study.

All concomitant medications will be recorded and analysed as described in [Section 20.4.3.3](#).

Not permitted

- Expectorants
- Antitussive agents
- Sedatives
- Traditional Chinese Medicine (TCM) treatments.

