10.7. VISIT 4 (DAY 7)

At Visit 4 (day 7), the following procedures will be performed:

- conduct dip-stick urine pregnancy test for females of childbearing potential.
- document concomitant medications;
- record details of any AEs since Visit 3 (day 3);
- assess of vital signs ([Section 11.1.3](#));
- conduct physical examination (including chest auscultation);
- give to patient the container for 24-hour sputum collection and instruct patient to collect all sputum until the same time of the following day;

- conduct assessment of expectoration difficulty, sputum viscosity, sputum color and cough by means of the 4-point ordinal scales provided.
- conduct 12-lead ECG in the supine position after 5 minutes of rest ([Section 11.1.6](#));
- collect blood samples for clinical laboratory assessments (haematology and clinical chemistry).
- to assess adherence with IMP dosing regimen
- administer study medication at the same times as on Day 1 (see Warning in section 10.2. above).

The Investigator will arrange an appointment for the follow-up call or visit 2 weeks \pm 3 days after the last administration of IMP

10.8. DAY 8

On day 8 the following procedure will be performed:

- collect 24-hour sputum sample and report volume (mL) in eCRF;

10.9. FOLLOW-UP PHONE CALL OR VISIT (2 WEEKS \pm 3 DAYS AFTER THE LAST ADMINISTRATION OF IMP)

A follow-up phone call will be performed at 2 weeks \pm 3 days after the last administration of IMP. If the patient is still hospitalized or it is more convenient for the patient, the follow-up call can be replaced by a follow-up visit

The following procedures will be performed during the follow-up call or visit:

- record details of any AEs since Visit 4 (day 7);
- record concomitant medications since Visit 4.

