13.2. INVESTIGATIONAL MEDICINAL PRODUCT DISPENSING AND ADMINISTRATION

All IMPs will be dispensed twice daily as one in the morning and another is in the afternoon/evening for a week of treatment period at hospital investigational sites by study staff. All IMP will be administered at the hospital investigational sites by study staff otherwise not involved with the efficacy assessment and care of study patients. The study staff members administering the IMP will be aware of its identity but will not disclose it to patients or to other study staff members who are involved in efficacy assessment (patient and rater-blind design, see [Section 4](#)).

NAC (Active test treatment)

Two ampoules (NAC 600 mg) will be diluted in 10 ml NaCl 0.9% saline solution and administered by slow (at least 5 minutes) intravenous infusion twice a day, morning before 9 am and afternoon/evening approximately 12 ± 1 hours apart for 1 week (7 days). Total daily NAC dose: 1200 mg/day.

Ambroxol hydrochloride (active control treatment)

Two vials (ambroxol 30 mg) will be diluted in 10 ml NaCl 0.9% saline solution and administered by slow (at least 5 minutes) intravenous infusion twice a day, morning before 9 am and afternoon/evening approximately 12 ± 1 hours apart for 1 week (7 days). Total daily ambroxol dose: 60 mg.

Placebo

One vial of 10 ml NaCl 0.9% saline solution will be administered by slow (at least 5 minutes) intravenous infusion twice a day, morning before 9 am and afternoon/evening approximately 12 ± 1 hours apart for 1 week (7 days).

Study staff administering the IMP will be instructed to store the empty used and the unused ampoules/vials for IMP accountability.

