16. CLINICAL TRIAL WITHDRAWALS/DROP-OUTS

Patients will be withdrawn from the trial for one of the following reasons:

- patient may withdraw from the study at any time at his/her own request;
- patient may withdraw from the study due to an AE;
- patient may be withdrawn at any time at the discretion of the Investigator for safety, behavioural, compliance or administrative reasons;
- patient may be withdrawn due to lack of adherence to study medication regimen.
- Female patient who becomes pregnant should be withdrawn from the trial and followed-up in accordance with [Section 18.8](#);
- Patient should be withdrawn from the trial once rescue mucolytic is received;
- non-emergency unblinding of study treatment allocation;
- lost to follow up: before a subject is deemed lost to follow up, the Investigator or designee must make every effort to regain contact with the participant (where possible, 3 telephone calls and, if necessary, a certified letter to the participant's last known mailing address or local equivalent methods). These contact attempts should be documented in the participant's medical record. Should the participant continue to be unreachable, he/she will be considered to have withdrawn from the study;

The sponsor, CA, or EC/IRB(s), can terminate the trial or participation of an individual site.

The reason for removal of a subject from the trial or premature discontinuation of treatment must be fully documented in the eCRF as well as in respective source documents. Follow-up for withdrawn subjects follows the procedures described in [Section 18.8](#) and [Section 18.9](#).

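### The dated ban on expectorants, antitussives, sedatives and TCM ends at Visit 4, before the Day 7 sputum collection is complete

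*Protocol*

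**What the plan says.** Protocol 12 lists four drug classes under this rule: "The following concomitant treatments are not permitted from Visit 1 to Visit 4 (end of IMP treatment) or unscheduled Deterioration Visit". SAP 4.7 uses the same window. The Protocol synopsis lists the same four classes as not permitted but gives no dates.

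At Visit 4 on Day 7, Protocol 10.7 tells staff to "give to patient the container for 24-hour sputum collection and instruct patient to collect all sputum until the same time of the following day". The task under Day 8 (Protocol 10.8) is to "collect 24-hour sputum sample and report volume (mL) in eCRF". The flow chart in Appendix 1 puts this collection in the Visit 4 column and notes that it is measured the next day. SAP 4.9.3 analyses the result as change from baseline to day 7 in sputum volume, for NAC against placebo and for ambroxol against placebo.

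Day 8 has no medication check. The next one is the follow-up call or visit in Protocol 10.9, where staff "record concomitant medications since Visit 4".

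SAP 4.7 defines concomitant medication up to the last dose, and prohibited concomitant medication follows that definition. The note to SAP 4.14.7.1 sets the category to missing for any drug started after the date of the last dose.

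**The concern.** The protocol bans these classes because they can change what the trial measures. For one measurement, the dated ban stops before the measuring does. A patient who is handed a container on the Day 7 morning could be given an ordinary expectorant, antitussive or TCM product that night or early on Day 8. Some of the sputum counted as the end-of-treatment volume would then be produced on that drug, and Protocol 12 read literally would not have been broken.

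If such starts were more common in one arm, the Day 7 volume contrasts with placebo could be distorted. Uneven use is conceivable: the warning in Protocol 10.2 groups patient care with the unblinded staff, although Protocol 13.2 separates drug administration from care. The planned by-arm table of prohibited medications would not show starts dated Day 8.

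**Working it through.** The plan gives no figure to reproduce on this point. The check compares dates.

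1. **Collection window.** It runs from hand-out at Visit 4 on Day 7 to the same time on Day 8 (Protocol 10.7 and 10.8). The synopsis says morning to morning. No clock time for hand-out is fixed.

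2. **End of the ban.** Protocol 12 and SAP 4.7 tie it to Visit 4 and the end of study treatment, without a clock time. Three readings are natural:
   - The Visit 4 morning assessment. The ban then ends about when the collection starts.
   - The last dose. The morning dose is before 9 am and the second follows 12 ± 1 h later (Protocol 13.2), so the last dose falls before 9 am + 13 h = 10 pm on Day 7.
   - The end of calendar Day 7, which is midnight.

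   All three come before the Day 8 morning. The order holds for any morning hand-out time.

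3. **Other rules.** The synopsis list has no end date, so it neither confirms nor extends the dated rule. The clause in Protocol 12 on interfering treatments sits in the same Visit 1 to Visit 4 window, and its discontinuation part refers only to the primary efficacy outcomes. Protocol 16 does apply after Visit 4, but only to rescue: "Patient should be withdrawn from the trial once rescue mucolytic is received". Elective use of a listed drug remains uncovered.

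4. **What the SAP would show.** A drug started on Day 7 has a start date no later than the last-dose date, so it can be tabulated. A drug started on Day 8 has a later start date, so the 4.14.7.1 note sets its category to missing and it leaves the prohibited-medication table. It would still be listed, because Protocol 20.4.1 makes all eCRF data available as listings.

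5. **When it is recorded.** Follow-up is 14 ± 3 days after the last dose. With that dose on Day 7, this is Day 7 + 11 = 18 to Day 7 + 17 = 24, or 10 to 16 days after Day 8. A start date may well be recovered then. A start time relative to container return may not be.

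6. **Reach.** Five efficacy variables at two post-baseline days give 5 × 2 = 10 endpoints. One of them, Day 7 volume, is touched, in two contrasts with placebo. The Day 7 scores are rated in the morning before dosing (Protocol 11.1.5), and the Day 3 collection ends on Day 4, inside the ban.

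7. **Early discontinuation.** Protocol 10.11 and the flow chart also call for a 24-hour collection at the premature discontinuation visit, and SAP 4.9.1.3 lets measurements from that visit feed the primary imputation. A ban that ended at that visit would leave the same gap. A patient withdrawn at a deterioration visit is also due the Visit 4 evaluations (Protocol 10.10), so that collection may run after rescue.

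**The case against.** The best defence is that Visit 4 need not end on Day 7. The flow chart treats the collection as a Visit 4 activity and has no Day 8 column, so a site could regard the visit as open until the container comes back. The undated synopsis list fits that reading. Against it, Protocol 12 glosses Visit 4 as the end of study treatment, and Protocol 10.8 gives Day 8 its own heading. The wording is therefore ambiguous, and this is why the point says only that use is not clearly barred. The Protocol Deviation Specification and the eCRF, both cited in SAP 1, are not among the documents. Whether such a start would count as a deviation, and whether start times are captured, is unknown.

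Three further objections stand and narrow the point:
- Rescue mucolytic leads to withdrawal with a documented reason, with no Visit 4 cut-off. Only elective use is left.
- Drugs taken since Visit 4 are asked about at follow-up and would be listed. A reader might infer that use on Day 8 would be untraceable, but the documents do not support that.
- Protocol 4 says only a small minority of patients receive intravenous mucolytics beyond one week, so elective starts of that kind may be uncommon.

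SAP 4.2 notes that baseline volume may be collected after the first dose. A reader might take the lack of a Day 7 counterpart as an inconsistency. It is not one: that text explains the timing of baseline and is not a medication rule.

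**Conclusion.** The point holds as a minor one. On its most natural reading, the dated ban in Protocol 12 and SAP 4.7 ends before the collection analysed as Day 7 sputum volume. Elective use of a listed drug in the last part of that collection is not clearly barred, and a Day 8 start drops out of the prohibited-medication table.

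A reader might go further in two ways, and neither is supported. The first is to convert the uncovered hours into a share of the collection and treat that as the size of the problem. The hand-out time and the exact end of the ban are not fixed, and hours outside a ban are neither drug exposure nor bias. With no rate of drug starts given, no size or direction can be stated. The second is to conclude that the efficacy claim is at risk. Day 7 volume is a non-key secondary endpoint tested without multiplicity adjustment (SAP 4.9.1.4). The co-primary endpoints, the non-inferiority test, sputum color, cough and the scheduled Day 3 volume are unaffected.

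The conclusion assumes that Visit 4 in the ban means Day 7 and that the unseen deviation specification does not already extend it.

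**What to change.** - **Ban.** In Protocol 12, the synopsis list and SAP 4.7, run it from Visit 1 until return of the last 24-hour sputum container: Day 8, or the day after a premature discontinuation visit. State that rescue treatment is allowed at any time and that any volume collected after rescue is flagged.
- **Table.** In SAP 4.7 and the 4.14.7.1 note, count a listed drug started up to container return as a prohibited medication in the by-arm table. The general definition of concomitant medication can stay as it is.
- **Check.** When the container is returned, ask whether a listed drug has been used.

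This needs no extra visit, container or analysis, and alpha and sample size do not change. The downside is about one more night of restriction on routine use of these drugs in hospitalised patients, including those on placebo. If the treatment phase is already over, the by-arm count can still be made from recorded start dates, with the caveat that a Day 8 date alone does not show whether the drug came before the container was returned.

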13. INVESTIGATIONAL MEDICINAL PRODUCT

13.1. INVESTIGATIONAL MEDICINAL PRODUCT SUPPLIES AND PACKAGING

NAC will be supplied in boxes containing 4 ampoules each.

NAC is formulated in yellow glass ampoules as a solution of 300 mg NAC in 3 ml water for injection; other excipients are: sodium hydroxide and disodium edetate. The product is manufactured by Zambon SpA, Vicenza, Italy.

Ambroxol hydrochloride will be supplied in boxes containing 4 vials each.

Ambroxol hydrochloride is formulated in yellow glass vials as a solution of 15 mg ambroxol hydrochloride in 2 ml water for injection; other excipients are: citric acid monohydrate, sodium hydrogen phosphate dihydrate, sodium chloride. The product is manufactured by Boehringer Ingelheim.

Placebo will be supplied in boxes containing 2 vials each.

Placebo is formulated in vials as 10 ml NaCl 0.9% saline solution. The product is manufactured by China Otsuka Pharmaceutical Co., Ltd.

13.2. INVESTIGATIONAL MEDICINAL PRODUCT DISPENSING AND ADMINISTRATION

All IMPs will be dispensed twice daily as one in the morning and another is in the afternoon/evening for a week of treatment period at hospital investigational sites by study staff. All IMP will be administered at the hospital investigational sites by study staff otherwise not involved with the efficacy assessment and care of study patients. The study staff members administering the IMP will be aware of its identity but will not disclose it to patients or to other study staff members who are involved in efficacy assessment (patient and rater-blind design, see [Section 4](#)).

NAC (Active test treatment)

Two ampoules (NAC 600 mg) will be diluted in 10 ml NaCl 0.9% saline solution and administered by slow (at least 5 minutes) intravenous infusion twice a day, morning before 9 am and afternoon/evening approximately 12 ± 1 hours apart for 1 week (7 days). Total daily NAC dose: 1200 mg/day.

Ambroxol hydrochloride (active control treatment)

Two vials (ambroxol 30 mg) will be diluted in 10 ml NaCl 0.9% saline solution and administered by slow (at least 5 minutes) intravenous infusion twice a day, morning before 9 am and afternoon/evening approximately 12 ± 1 hours apart for 1 week (7 days). Total daily ambroxol dose: 60 mg.

Placebo

One vial of 10 ml NaCl 0.9% saline solution will be administered by slow (at least 5 minutes) intravenous infusion twice a day, morning before 9 am and afternoon/evening approximately 12 ± 1 hours apart for 1 week (7 days).

Study staff administering the IMP will be instructed to store the empty used and the unused ampoules/vials for IMP accountability.

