This trial is designed as rater- and patient-blind. i.e. whereas the staff administering the study drugs will know what each patient is receiving, neither the staff evaluating the patient, nor the patients themselves will know. The trial cannot be fully blinded (double-blind) because the appearance of NAC ampoules and ambroxol vials is different and more importantly because the NAC formulation releases a harmless but immediately distinguishable sulfuric smell. Rater- and patient-blinded designs are accepted for pivotal registration trials by the US-FDA, EMA and Regulatory Authorities worldwide in situations where full blinding is impossible.

The selected doses of iv NAC and ambroxol are within the limits of relevant SmPCs (10,18); dose justification is provided in [Section 5](#) below.

The treatment duration of 1 week has been selected after consultation with Chinese experts, as only a small minority of patients receive iv mucolytics for more than 1 week.

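### As written, the three arms are infused in different volumes (16, 14 and 10 ml) with nothing to match or hide them, which could give patients an avoidable cue to active drug against placebo.

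*Protocol*

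**What the plan says.** Protocol version 2.0, Section 13.1, gives the container volumes: "NAC is formulated in yellow glass ampoules as a solution of 300 mg NAC in 3 ml water for injection", and "Ambroxol hydrochloride is formulated in yellow glass vials as a solution of 15 mg ambroxol hydrochloride in 2 ml water for injection". Placebo is a 10 ml vial of 0.9% saline.

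Section 13.2 gives the preparations:

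- NAC: "Two ampoules (NAC 600 mg) will be diluted in 10 ml NaCl 0.9% saline solution".
- Ambroxol: "Two vials (ambroxol 30 mg) will be diluted in 10 ml NaCl 0.9% saline solution".
- Placebo: "One vial of 10 ml NaCl 0.9% saline solution will be administered by slow (at least 5 minutes) intravenous infusion twice a day".

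The Summary describes the same three preparations. All arms carry the same minimum time of five minutes; no common rate, duration or final volume is given.

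On blinding, Section 4 says that "neither the staff evaluating the patient, nor the patients themselves will know". It names container appearance and the NAC smell as the obstacles to a full double blind, and the SAP Introduction repeats these two. Neither mentions volume. Section 13.2 relies on non-disclosure: staff giving the drug "will be aware of its identity but will not disclose it to patients or to other study staff members who are involved in efficacy assessment". Section 13.4 refers to Section 4 for instructions on maintaining the blind, but Section 4 only explains why a double blind is impossible. The SAP plans no check that the blind held.

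**The concern.** Each active dose is added to 10 ml of saline, and placebo is the 10 ml alone. Volume, and with it rate or duration, therefore depends on the arm. Non-disclosure by staff does not hide this from a patient watching the infusion. Patients are hospitalised and randomised in blocks within site (13.3), so some may be able to compare infusions.

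The clearest difference, active against placebo, falls on the primary contrast. It also falls on ambroxol against placebo, which 20.4.3.2 uses to verify assay sensitivity and for which no smell cue is stated.

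There are two routes from a suspicion to the result, both through the patient:

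1. Expectoration difficulty is a 4-point rating that plausibly depends on what the patient reports, and success on one co-primary score is enough (20.2).
2. A patient who suspects placebo can take part in the decision to receive rescue and leave (8.1, 10.10). Missing scores are then replaced by the worse of baseline and later values (Protocol 20.4.4, SAP 4.9.1.3). That allows no improvement on either co-primary score, and this route does not need the rater to be influenced.

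**Working it through.** **Container counts, checked against the stated doses (13.1, 13.2).** NAC: 2 × 300 mg = 600 mg, × 2 = 1200 mg/day. Ambroxol: 2 × 15 mg = 30 mg, × 2 = 60 mg/day. Both agree with the protocol, so two containers per infusion is the right count.

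**Infused volume = containers × ml per container + 10 ml saline.** The last two columns show the rate if every arm runs for the five-minute minimum, and the duration if every arm runs at 2 ml/min. That rate is assumed; it delivers 10 ml in 5 minutes.

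| Arm | Volume | Against placebo | Rate at 5 min | Time at 2 ml/min |
|---|---|---|---|---|
| NAC | 2 × 3 + 10 = 16 ml | +6 ml (60%) | 3.2 ml/min | 8 min |
| Ambroxol | 2 × 2 + 10 = 14 ml | +4 ml (40%) | 2.8 ml/min | 7 min |
| Placebo | 10 ml | – | 2.0 ml/min | 5 min |

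A common time gives different rates, and a common rate gives different times. NAC and ambroxol differ by only 2 ml, a weak cue.

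**Exposure before the co-primary rating.** Ratings are made before the morning dose (11.1.5), so days 1 to 6 count: 6 × 2 = 12 infusions before the day 7 rating, and 2 × 2 = 4 before day 3.

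**How much a bias would matter, if there were one.** Inputs: SD 0.77 for expectoration difficulty and 111 per arm (20.3), one-sided 0.0125 (20.4.5). Normal approximation, no true effect.

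- SE = 0.77 × √(2/111) = 0.103; critical z = 2.241.
- Shift 0.05 (for example, 5% of NAC patients moved by one point): 0.05/SE = 0.484; 1 − Φ(2.241 − 0.484) = 0.039.
- Shift 0.10: 0.10/SE = 0.968; 1 − Φ(2.241 − 0.968) = 0.101.

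**Both co-primaries together.** With 100 per arm, difference 0.35, SDs 0.79 and 0.77 and correlation 0.31, a Mann-Whitney simulation of 4000 runs gives disjunctive power 92.9%, against the plan's figure of close to 93%. A bivariate-normal version of the same set-up (93.6%) puts the chance of a false primary success at 2.4% with no shift. It rises to 6.8% with 0.05 points, and 15.7% with 0.10 points, on both scores.

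**The case against.** The strongest reply is that a difference in volume is not unblinding. In a parallel-group design each patient sees one volume, and nothing in the documents available here tells patients which volume belongs to which arm. The cue works only for someone who compares infusions, or knows the volumes, and also takes the larger one to be active. Scores are given by a blinded rater who is not the administering staff (10.2) and who rates before the morning dose. Viscosity is scored on sputum descriptors, and the documents do not say how expectoration difficulty is elicited. Section 4 also admits an NAC smell that equal volumes would not remove.

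All of this stands, and it limits the conclusion. A reader might infer from the volumes that the blind is broken, or that both active-placebo comparisons are biased upward. The documents do not support that: they show a possible cue, not its recognition, its direction or its effect.

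It might also be said that diluting in 10 ml was meant as making up to 10 ml. The text does not say so, and Appendix 2 names a final volume explicitly when it describes aerosol dilution. If that was the intention, 13.2 and the Summary still need correcting.

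The admitted smell does not answer the point either. It concerns NAC only, and an unavoidable cue is no reason to keep an avoidable one.

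**Conclusion.** The point holds as a correctable design weakness. The 16, 14 and 10 ml follow directly from 13.1, 13.2 and the Summary. No text in the protocol or SAP matches or conceals volume or infusion time, and the blinding instructions promised in 13.4 are missing. Volume can therefore give patients a cue, chiefly active against placebo.

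Whether it would bias the result, and by how much, is unknown. The error rates of about 4% and 10% rest on assumed shifts of 0.05 and 0.10 points and on a normal approximation in place of the planned baseline-stratified rank test on 4-point scores. They show that a small bias would matter, not that one exists. It is also an assumption that patients could compare infusions.

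**What to change.** Reconcile the Summary and Sections 4, 13.1, 13.2 and 13.4, so that the protocol:

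- states the final infused volume in each arm;
- has the administering staff, who are already unblinded, make the infusions indistinguishable to the patient in volume and infusion time, either matched with saline or concealed, with drug amounts unchanged and the values left to the sponsor's pharmacist;
- contains in Section 4 the blinding instructions to which 13.4 refers.

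No conflict with Appendix 2 or 3 has been shown, and no dose, volume or infusion time is proposed here.

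The cost is protocol wording and slightly more preparation per dose. If volumes are matched above 10 ml, each placebo dose needs saline beyond its single vial, with extra supply and accountability entries. The NAC smell would remain, so the fix removes one cue and not every cue.
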